#### 11.1.2 Definition of Serious Adverse Event

A serious adverse event (SAE) is an adverse event that, at any dose of study drug, results in:

- Means a patient died; or
- Life-threatening; or
- Required or prolonged hospitalization; or
- Results in persistent or significant disability or incapacity; or
- Results in congenital anomaly or birth defect;
- Other medically important event:

Note: The term "life-threatening" in the definition of "serious adverse event" refers to an event in which the patient is at immediate risk of death from the event; it does not refer to an event that hypothetically might have caused death if it were more severe.

Hospitalization or prolongation of hospitalization will not be considered an adverse event if the following conditions are met: hospitalization planned before enrollment in the study; a mobile hospitalization (12 hours); a hospitalization that is part of the normal treatment or monitoring of the disease under study but is not caused by a worsening of the disease; a hospitalization that is only related

to socioeconomic factors and not related to the disease (e.g., hospitalization for medical insurance reimbursement, accommodation problems or physical examination needs).

#### 11.2 Classification of adverse events

#### 11.2.1 Severity of adverse event

All adverse events will be graded for severity according to the International System for Assessment of Adverse Drug Reactions to Cancer chemotherapy CTCAE v4.03 and refer to the details reported on the eCRF. In the event of any death, an appropriate death report form was completed. If an adverse event occurred that was not included in the NCI-CTCAE, it was graded using a quintile scale (mild, moderate, severe, life-threatening, death), 9.

#### **Table 9: Adverse Event Severity Grading**

Mild	Discomfort but no effect on normal daily activities
Moderate	Discomfort sufficient to reduce or affect daily activities
Severe	Inability to work or perform normal daily activities
Life Threatening	Immediately life-threatening
Death	Death related to AE

# 11.2.2 Relationship of adverse event to study drug

The investigator should determine the causality of adverse drug event/reaction and analyze the correlation. The analytical methods used mainly follow the following five principles (see Table 10).

Table 10: Relationship between adverse reactions and study drug

Serial number	Problem	Yes	None	Unknown
1	Whether there is a reasonable temporal relationship between medication and the occurrence of adverse reaction/event?			
2	Whether the reaction conforms to the known type of			

	adverse reaction of the drug?		
3	Did the reaction/event disappear or abate after stopping the drug or reducing the dose?		
4	Did Reaction/Event Reappear After Reintroduction of Suspect Drug?		
5	Can the reaction/event be explained by the effect of concomitant medication, progression of the patient's condition, effect of other therapies?		

Relevance evaluation: According to the above five principles of adverse event/reaction analysis, the relevance evaluation is classified as positive, probable, possible, unlikely and unrelated (see Table 11).

Table 11: Relatedness of Adverse Events to Study Drug

	Question 1	Question 2	Question 3	Question 4	Question 5
Definitely related	+	+	+	+	-
Probably related	+	+	+	?	-
Possibly related	+	±	±?	?	±?
Unlikely related	-	-	±?	?	±?
Unrelated	-	-	-	?	+

Note: + indicates yes; - indicates no;  $\pm$  indicates it is difficult to judge yes or no;? Indicates unknown;

Questions 1, 2, 3, 4, 5 10.

The determination of correlation between adverse events and drug is the result of individual judgment by the investigator. When the principal investigator summarizes the clinical trial data and summarizes the safety data, the overall judgment shall be made according to the drug ingredients, dosage regimen, results of preclinical safety study, frequency, severity and trend of adverse events.

#### 11.3 Frequency and duration of adverse events

The frequency and duration of adverse events should be recorded and reported in the eCRF.

#### 11.4 Adverse event monitoring

The monitoring and reporting of adverse events is a necessary item in the daily work of clinical trials. All adverse events must be managed and reported in accordance with applicable regulations and applicable regulatory requirements and included in the final study report.

# 11.5 Recording and reporting of adverse events

#### 11.5.1 AE recording

1368

1371

1372

13731374

1375

1376

1377

1378

1379

1380

1381

13821383

1384

1396

1397

1398

All adverse events, regardless of severity or relationship to the study product, shall be recorded in the EDC system from the signing of the informed consent form at the first visit scheduled in the clinical trial protocol, throughout the study treatment period and post-treatment evaluation period (within 21 days after the last administration of the study drug). Even if the subjects have completed the study treatment, they must be followed up until the adverse event is completely relieved or the event can be fully explained. The records shall include:

- Event name;
- Onset date and duration (start and stop times, or ongoing at visit);
- Severity (mild, moderate, severe or grade);
- Relationship to the study drug (definite, probable, possible, unlikely related, to be evaluated);
- Whether the investigational drug is stopped;
- AE action taken:
- Outcome (disappearance, remission, persistence, aggravation, death).
- The investigator should take appropriate measures to ensure the health and safety of the subjects according to the AE; the specialized ward should ensure the supply of relevant rescue equipment and drugs to ensure timely treatment in case of emergency.

### 11.5.2 SAE Reporting

Any SAE occurring during the trial (whether or not related to the investigational product) should be reported to Shanghai Miracogen Inc., Covance PV & Drug Safety,

clinical study institution and its Ethics Committee by fax/email within 24 hours and reported to China Food and Drug Administration.

Contact information for SAE report:

Covance Pharmacovigilance and Drug Safety: [contact]

All SAEs were to be followed up by the investigator until the final outcome was known. The investigator should fill in the SAE form for tracking, tick the "Follow-up Report" or "Final Report" column and fax/email it to Covance PV & Drug Safety, Clinical Trial Institution, Ethics Committee and China Food and Drug Administration. The frequency of follow-up was determined by the investigator on a case-by-case basis.

Note: For general AE events, medical and scientific judgment should be exercised in deciding whether expedited reporting is appropriate within 24 hours, such as important medical events that are not immediately life-threatening or result in death or hospitalization but may jeopardize the patient or may require intervention to prevent further outcomes in the definition of SAE. Some examples of such events are: treatment in a Phase I clinical trial ward, asymptomatic ALT elevations  $\geq 10 \times \text{ULN}$  due to allergic bronchospasm, cachexia, convulsions, or do not result in hospitalization, or development of drug dependency or drug abuse.

#### 11.5.3 Drug-induced liver injury

Drug-induced liver injury is one of the most common and serious adverse drug reactions, and can cause acute liver failure or even death in severe cases. Hy's rule has important reference value for judging the prognosis of drug-induced liver injury. The core content is: in clinical trials, if there are subjects with serum ALT or AST  $\geq$  3 ULN and total bilirubin  $\geq$  2 ULN (not necessarily at the same time), it meets the potential Hy's law. If the subject meets potential Hy's Law and there is no other reason than the investigational product to explain the increased laboratory values. Alternative causes may include cholestasis, viral hepatitis, or other drug effects as indicated by elevated alkaline phosphatase (ALP). If the investigator identifies a potential Hy's Law case, the SAE Report Form should be completed and reported to the sponsor (or its designee) in an expedited manner within 24 hours. The investigator should then assess whether the case meets Hy's law and will report the results.

#### 11.5.4 Serious Adverse Events Due to Disease Progression

Serious adverse events due to disease progression for all subjects treated with MRG003 should be reported according to the SAE reporting requirements within 21 days after signing the informed consent form at the first visit scheduled in the clinical trial protocol, throughout the study treatment period, and after the last dose of the study drug.

Serious adverse events due to disease progression that occur during the efficacy and survival follow-up periods of 21 months after the last dose of study drug do not need to be reported as SAEs.

### 11.5.5 Death

Any death, including death due to tumor progression, that occurs within 21 days of signing of informed consent and following the last cycle of study drug administration must be reported within 24 hours to a monitor appointed by the sponsor representative, regardless of the relationship between the death and the study drug. If a death occurs during the efficacy and survival follow-up periods, only those reports need to be considered serious if the relationship to study drug is deemed possible. All deaths should be recorded in the death report section of the eCRF, regardless of the causal relationship with the study drug.

## 11.5.6 Pregnancy

- In all cases, the pregnancy should be recorded and a pregnancy report should be completed.
- The Investigator should inform the patient (or legal representative) of the risks of continuing the pregnancy and the possible effects on the fetus.
- Female patients must be instructed that if they become pregnant during the study, they must discontinue any study medication and immediately report to the investigator. Pregnancies occurring within 90 days of completion of study drug must also be reported to the investigator. The investigator should report to the sponsor (or its designee) in an expedited manner within 24 hours.
- Any pregnancies in the partner of a male patient participating in the study should also be reported immediately to the investigator, who will also report in an expedited manner according to the procedures described above.
- The pregnancy must be followed up until the outcome is determined.

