#### Liver and kidney function:

- Total bilirubin  $\leq 1.5 \times$  upper limit of normal (ULN);
- ALP ≤ 1.5 times ULN. If the patient has bone metastasis, ALP has no upper limit;
- AST and ALT: ≤ 2.5 times ULN for patients without liver metastasis or ≤ 3 times ULN for patients with liver metastasis;
- International normalized ratio < 1.5 times ULN (anticoagulant naïve) or international normalized ratio < 3 times ULN (anticoagulant naïve);
- Serum creatinine  $\leq 1.5$  times ULN;
- 10) Women of childbearing age must have a negative serum pregnancy test before entering this study and agree to take complete contraception from the beginning of the study to at least 6 months after administration of the study drug; female patients without childbearing potential should have spontaneous amenorrhea for at least 12 months; or have undergone oophorectomy, hysterectomy or tubal ligation more than 6 weeks before screening; in the case of unilateral oophorectomy, their fertility status will be determined by hormone levels;
- 11) Male patients must agree to take effective contraceptive measures (male condom with spermicide, or provide evidence of successful vasectomy;

non-fertile sexual partner, or female partner using intrauterine device with spermicide, female condom with spermicide, contraceptive sponge with spermicide, intravaginal contraception, diaphragm with spermicide, cervical cap with spermicide, or oral/implantable/topical or injectable contraceptives;

12) Patients voluntarily signed the written informed consent form to participate in this clinical trial, following the study schedule and other requirements of the protocol.

Patients must not enter the study if any of the following exclusion criteria are fulfilled:

- 1) History of allergic reaction to any component of MRG003;
- 2) Patients with symptomatic central nervous system (CNS) metastases;

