#### 7.3 Inclusion criteria

- 699 Gender: Male or female;
- 700 2) Age:  $\geq 18$  years,  $\leq 75$  years;
- 701 Life expectancy  $\geq 12$  weeks;
- 702 Phase Ia dose escalation phase: patients with histologically or cytologically confirmed
- 703 locally advanced or metastatic solid tumors who have failed or cannot obtain standard
- treatment; 704
- 705 Phase Ib dose expansion phase: patients with histologically or cytologically confirmed
- 706 locally advanced or metastatic colorectal cancer, head and neck squamous cell
- 707 carcinoma or nasopharyngeal carcinoma, who have failed standard treatment, cannot
- tolerate standard treatment or cannot obtain standard treatment; 708
- 709 For patients participating in phase Ib clinical trial, their pathological samples shall be
- positive for EGFR expression by immunohistochemical detection; 710
- 711 Patients must have at least one measurable lesion as defined by RECIST v1.1;
- 712 ECOG score of 0-1;
- 713 Patient has organ function meeting the following laboratory test results at baseline
- 714 examination at the time of enrollment:
- 715 Blood function
- 716 Absolute neutrophil count  $\geq 1.5 \times 109/L$ ;
- 717 Platelets  $\geq 100 \times 109/L$ ;
- 718 Hemoglobin  $\geq 9 \text{ g/dL}$ ;
- Hepatic and renal function: 719
- 720 Total bilirubin  $\leq 1.5 \times \text{upper limit of normal (ULN)};$
- 721  $ALP \le 1.5$  times ULN. If the patient has bone metastasis, ALP has no upper
- 722 limit;

- AST and ALT: ≤ 2.5 times ULN for patients without liver metastasis or ≤ 3
   times ULN for patients with liver metastasis;
- International normalized ratio < 1.5 times ULN (anticoagulant naïve) or international normalized ratio < 3 times ULN (anticoagulant naïve);
- Serum creatinine ≤ 1.5 times ULN;
- 728 10) Women of childbearing age must have a negative serum pregnancy test before 729 entering this study and agree to take complete contraception from the beginning of the 730 study to at least 6 months after administration of the study drug; female patients 731 without childbearing potential should have spontaneous amenorrhea for at least 12 732 months; or have undergone oophorectomy, hysterectomy or tubal ligation more than 6 733 weeks before screening; in the case of unilateral oophorectomy, their fertility status 734 will be determined by hormone levels;

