- Male patients must agree to use effective contraceptive measures (male condom with spermicide, or provide evidence of successful vasectomy; an intrauterine device with spermicide, female condom with spermicide, contraceptive sponge with spermicide, intravaginal contraceptive, diaphragm with spermicide, cervical cap with spermicide, or oral/implanted/or injectable contraceptives) from the start of the study to at least 6 months after study drug administration;
- 741 12) Patients voluntarily signed the written informed consent form to participate in this clinical trial, followed the study schedule and other requirements of the protocol.

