- (i) Serum pregnancy testing was performed on female subjects throughout the study and 21 after the dosing period.
- (j) Includes: HIV (anti-HIV antibody) testing and hepatitis B virus (HBsAg) and hepatitis C virus antibody (anti-HCV antibody) testing.
- (k) For MRG003 intravenous drip, see Section 9.3.
- (1) Detailed plan for PK blood sampling 7-1, 7-2 and Table 8. Of these, Day 5 only has visit schedule in Phase Ia.
- (m) Disposable blood sampling for PK and ADA measurements at the Day 21 visit after the end of dosing.
- (n) Blood anti-therapeutic drug antibody (ADA) concentrations were measured in all subjects. In addition to the above table, ADA concentrations will also be tested before the start of the follow-up period at the end of the dosing period, see Table 7.
- (o) Tumor tissue samples are used for biomarker detection and genetic testing of subjects.
- (p) See Section 6.3.4 for evaluation of MTD.
- (q) Subjects will be evaluated for tumor response every 6 weeks (at the end of the double dose cycle, i.e., before the start of the next dose cycle), and if a subject experiences a CR or PR, confirmation by the same method should be performed 6 weeks later.
- (r) For efficacy assessments of PFS, DOR, and OS, see Section 6.5.
- (s) Physical examination included head and neck, skin, lymph nodes, thyroid, musculoskeletal, extremities, cardiovascular, respiratory, abdominal, and neurological systems, and was performed only on the first day of the

	Pre- screening period	Screeni ng Period						,	Treatmen	t period						Postdose Assessme nts		cy and Follow-up
Visit Item	Pre- screening	Screeni ng		Cycle 3 and subsequent cycles x												After administr ation	Every 6 weeks	Every 12 weeks
Scheduled Time Node (days)	D-42	D-28 c	D1 d	D2 D3 D4 D51 D8 D11 D15 D1 D2 D8 D15 D1										D21				

cycle after Cycle 3. Photographs can be taken and archived locally on the skin of representative lesions.

- (t) Ophthalmic examination Ocular examination, including visual acuity, slit-lamp examination and dry eye examination such as tear secretion test, is only performed by ophthalmologists during the screening period and when ocular adverse reactions occur as needed.
- (u) Blood samples for carcinoembryonic antigen were collected from all colorectal patients before administration on the first day of each odd cycle (1, 3, 5, 7).

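### For female patients, the stated duty to report a pregnancy after treatment ends at 90 days, about half of the contraception period of at least 6 months

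*Protocol*

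**What the plan says.** **Reporting.** Section 11.5.6 tells female patients to stop study medication and notify the investigator at once if they become pregnant during the study. It then adds: "Pregnancies occurring within 90 days of completion of study drug must also be reported to the investigator". The investigator must pass the report on within 24 hours.

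The other bullets of 11.5.6 carry no time limit. The section opens with "In all cases, the pregnancy should be recorded and a pregnancy report should be completed" and closes by requiring follow-up until the outcome of the pregnancy is known. For men it says: "Any pregnancies in the partner of a male patient participating in the study should also be reported immediately to the investigator".

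**Contraception.** Synopsis inclusion criterion 10 requires that women of childbearing age "agree to take complete contraception from the beginning of the study to at least 6 months after administration of the study drug". Section 7.3 repeats the period for women ("study to at least 6 months after administration of the study drug"). For men, section 7.3 criterion 11 gives "from the start of the study to at least 6 months after study drug administration"; the synopsis version of that criterion shows no duration.

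**Detection after treatment.** A footnote to Table 6 in section 9.1 reads: "Serum pregnancy testing was performed on female subjects throughout the study and 21 after the dosing period". The unit is missing, but the table places the last test at the day-21 post-dose visit. Section 11.5.1 records adverse events up to the end of the "post-treatment evaluation period (within 21 days after the last administration of the study drug"). Sections 6.5 and 9.7 describe later follow-up as tumour assessment and survival contact. The items that 6.5 asks sites to record there are whether the patient is alive and what further anticancer treatment was given. Pregnancy is not among them.

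**The concern.** The contraception criterion implies that the sponsor wants pregnancy avoided for at least 6 months after study drug. The only post-treatment reporting period given to female patients ends after about half of that time. In the remaining months a patient is still asked to avoid pregnancy but is no longer explicitly asked to report one.

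What is at stake is safety information, not an efficacy or dose-finding result. The trial is first-in-human, and section 4.2.2.1 describes a payload that blocks tubulin polymerization and mitosis. The protocol itself treats pregnancy as a matter for 24-hour notice and follow-up to outcome. If the trigger for that process ends early, a relevant pregnancy may never reach the investigator.

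**Working it through.** No sample size, power or error rate is involved. The check compares two stated periods and then asks whether anything else in the protocol covers the difference.

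**Inputs**
- Reporting window, female patients: 90 days after completing study drug (11.5.6).
- Contraception period, women: at least 6 months after study drug (synopsis criterion 10; 7.3 criterion 10).
- Last scheduled pregnancy test: day 21 after dosing, visit window 7 days (Table 6).
- End of adverse event recording: 21 days after the last dose (11.5.1).
- Assumption: 6 months is 180 days (6 × 30) to 184 days (the longest run of six calendar months).

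**Length of the gap, both periods counted from the same day**
- Uncovered days = contraception period − reporting window: 180 − 90 = 90 days; 184 − 90 = 94 days.
- Share covered: 90/180 = 50%; 90/184 = 49%.
- Share uncovered: 90/180 = 50%; 94/184 = 51%.

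Because the criterion says at least 6 months, these are minimum gaps under the common start.

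**Sensitivity to the starting point.** One clause counts from completion of study drug, the other from its administration. If completion were read as the end of the last 21-day cycle, the reporting window would close 21 + 90 = 111 days after the last dose. The gap would be 180 − 111 = 69 to 184 − 111 = 73 days, or 38% (69/180) to 40% (73/184). It shrinks but does not close.

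**Does another procedure cover the interval?**

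| Days after last dose | Scheduled pregnancy test | Routine adverse event recording | Explicit duty on the patient to notify |
|---|---|---|---|
| 0 to 21 | Yes, at day 21 (± 7) | Yes | Yes |
| 22 to 90 | None after the day-21 visit | No | Yes |
| 91 to about 180–184 | None | No | No |

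In the last row only the visits and contacts of sections 6.5 and 9.7 remain, every 6 or 12 weeks, and pregnancy is not a listed item. Detection there depends on the patient volunteering the information without being told that she must.

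**Partners of male patients.** The partner bullet has no end date. Its reference to the procedures above it most naturally means the expedited report, not the 90-day limit. There is no shorter window to subtract, so no gap can be computed.

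**The case against.** The strongest case on the other side has four parts.

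1. *The two periods govern different things.* One concerns the patient's behaviour and the other her duty to report, and a site can comply with both. This stands: the periods are misaligned, not strictly contradictory. The protocol also never calls the 6 months a risk period.

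2. *Section 11.5.6 still requires recording and follow-up.* A reader might infer that a pregnancy after day 90 would produce no report and no follow-up of its outcome. The documents do not support that. The opening and closing bullets have no time limit and can apply to any pregnancy that becomes known. They do not, however, tell a patient to come forward after day 90. If they did, the 90-day sentence would have no purpose.

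3. *Pregnancy during the study may include long-term follow-up.* This is possible, since contact continues until the patient dies or the study ends. But the same sentence tells the patient to stop study medication, and the next adds 90 days after completion as something further. Both point to the treatment period.

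4. *The event is rare and changes no analysis.* This stands. About 26 + 36 = 62 patients are planned, all with advanced cancer, and women of childbearing age need a negative test and must agree to contraception. The protocol supports no estimate of expected pregnancies. The percentages above describe time, not events.

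A reader might also extend the gap to partners of male patients. Their rule covers any pregnancy without an end date, so the text shows no gap there.

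**Conclusion.** The point holds for female patients, in a limited form. The explicit post-treatment reporting duty covers 49% to 50% of the minimum contraception period. At least 90 to 94 days are left with no stated duty to notify and no scheduled means of detection. This assumes that both periods start on the same day and that 6 months is 180 to 184 days; on the later start for the reporting window the gap is 69 to 73 days.

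The text does not show that late pregnancies must go unrecorded. Nor does it imply that such a pregnancy is a breach of the protocol, since contraception can fail. DLT assessment, the MTD or RP2D, response rate and the analysis sets are untouched. The point is still worth correcting, because a safety rule followed as written stops short of the protocol's own contraception period, no reason is given, and the remedy is cheap.

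**What to change.** Reconcile section 11.5.6 with inclusion criterion 10 in section 7.3 and the synopsis, so that the explicit reporting window for female patients is not shorter than the contraception period the protocol finally states. Which length that should be is for the sponsor to decide. Count both periods from the same defined event, and carry the result into the consent wording so that patients know how long they are asked to notify.

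Two clarifications could go into the same edit, though the point does not depend on them: an explicit period for partner pregnancies, and agreement between the synopsis and section 7.3 on the duration for men.

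The cost is protocol and consent text and a longer period in which a rare event must be notified. No visit or test is added.
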